The primary analysis will compare change in accuracy of naming untrained items between groups (A-tDCS versus sham) in a two-sample *t*-test for the Intent-to-treat sample. For participants who do not complete the Week 1 post-treatment assessment, the post-treatment value will be imputed using a multiple imputation approach assuming a monotone missing mechanism and missing is at random (MAR). As a sensitivity analysis, the primary outcome analysis will be repeated using all available follow-up data (without explicit imputation) in a mixed effects model of the change from baseline in naming accuracy adjusted for baseline (with Week 1, 5, or 20 as a categorical variable and a random effect for subject). Similar analyses will be done for the change in accuracy of trained items.

If we accept the null hypothesis, then tDCS is considered clearly ineffective (in improving anomia in stroke patients) and will not be considered for further study. If we reject the null hypothesis, we would consider undertaking a Phase III study of tDCS.

Sample Size Determination

We expect to enroll 50 participants over 4 years, and expect 40-45 will complete the study. We predict no difficulty recruiting at least 10-15 participants with aphasia each year after subacute stroke, as the PI has

Date: March 2, 2021

Principal Investigator: [name], MA

Application Number: IRB00089018

recruited an average of 53 aphasic patients due to acute left hemisphere ischemic stroke each year in her previous studies of aphasia recovery. If sample size in each group is 20, (a total sample size of 40), we will have 89% power to detect a difference in means of 23 (the difference between a A-tDCS mean change in accuracy, μ_1 , of 33 and a sham mean change in accuracy, μ_2 , of 10) assuming that the standard deviation of change for both groups is 22.2 using a two group *t*-test with a two-sided alpha of 0.05. These mean changes for tDCS and sham and standard deviation of change are based on the one published sham-controlled study of tDCS combined with SALT in subacute stroke.

Multiplicity

Since this is a Phase I/II study, the false positive error rate has been relaxed (Schoenfeld, 1980). For a futility design the type I and type II error rates are reversed as compared to a traditional, superiority hypothesis. For the primary analysis, the probability of incorrectly declaring a drug futile is 0.1 (or 10%, type I error is the false negative rate). Given that the active tDCS comes from a distribution with a mean change of the control group (e.g. the treatment is the same as the sham), the probability of incorrectly moving to a Phase III trial is 0.15 (or 15%, type II error is the false positive rate).

For secondary outcomes and safety analyses, no adjustment of Type I error probability will be considered, since they will be treated as exploratory.

Missing Data

Under the ITT principle, all patients who are randomized are included in the analysis. Therefore, missing data, especially in the primary outcome measure, can be problematic. For the primary futility analysis we will impute missing data using multiple imputation (Rubin, 1987) assuming a monotone missing mechanism and missing is at random (MAR). Similar methods will be employed for secondary analyses and secondary outcomes. For safety data (e.g. AEs) no data imputation will be done.

Interim Analysis

No formal interim analyses are planned.

Adjusting for Covariates

The primary analysis will be adjusted for aphasia type, and baseline aphasia severity (AQ), education, time from stroke onset to time of treatment initiation, and number of previous SLP treatment sessions (prior to our study).

Secondary Analyses

In addition to the primary outcome, several secondary analyses will be conducted. We will examine changes in types of naming errors (defined by the PNT) by tDCS treatment group. The Cinderella story will be analyzed by comparing lexical diversity (VOCD) for nouns, verbs and adjectives; number and types of errors; length and patterns of pauses by treatment group. Pre and post comparisons with both non-aphasic and aphasic speakers from the Aphasia Bank database who share a number of demographic features (e.g., type and severity of aphasia, age, etc.) will also be made. We will also evaluate differences between treatment groups in QOL as measured by the Stroke Impact Scale, mRS, Content Units (CU) and syllables/CU in describing the Cookie Theft picture on the NIH Stroke Scale.

At the end of the study, for the interval scale variables, mean change from baseline to immediate

Date: March 2, 2021

Principal Investigator: [name], MA

Application Number: IRB00089018

post-testing in secondary outcome measures will be reported by treatment group along with the 95% confidence intervals. Treatment comparisons will be made with a paired t- test. For binary variables, the proportion of subjects immediately post-testing will be reported by treatment group along with the 95% confidence intervals.

Post-Testing Phase

The longer follow-up post-testing phase will provide exploratory information on whether the immediate post-testing improvement after three weeks of treatment can be sustained. The mean (95% CI) changes from baseline to immediate (within one week) post-testing, five weeks (after the end of treatment) post-testing and 20 weeks (after the end of treatment) post-testing will be reported. Box and whisker plots will be produced to show the distribution of naming accuracy over time by treatment group. To explore the longitudinal data, a general linear mixed model (GLMM) will be constructed by tDCS group for the dependent variable (anomia). The GLMM will incorporate random subject effects to account for repeated measurements being made on subjects; the model will include time, aphasia type, severity, and clinical center as independent variables. A similar modeling approach may be applied to other secondary outcomes.

Safety Analyses

All adverse experiences will be summarized in terms of frequency, severity and relatedness to the study treatment using the MedDRA code. All subjects who received tDCS will be included in the safety analysis. At the end of the study, the cumulative incidences of adverse events are compared between the two treatment groups using Fisher's exact test at the two-sided alpha level of 0.05.

The repeated measures of the FACES pain rating scale will be compared by treatment group by fitting a repeated measures proportional odds model.

DSMB Reporting

The study biostatistician will generate closed and open DSMB reports semi-annually or more frequently, as determined by the DSMB. Each DSMB report provides cumulative summary statistics on enrollment; subject status in the study (e.g., number completed study, drop outs, etc.); baseline characteristics; safety data, including AEs and SAEs; and data quality information. The statistics for the closed DSMB Reports are provided by treatment group displayed as A or B. The open report contains aggregated statistics only, i.e., not by treatment group.

d. Early stopping rules. N/A

8. Risks

a. Medical risks, listing all procedures, their major and minor risks and expected frequency.

tDCS

The present study involves application of transcranial direct current stimulation. Weak direct currents can be applied non-invasively, transcranially and painlessly (Nitsche et al., 2003; Priori et al., 2009). This is a non-invasive and painless technique that leads to transient changes in cortical excitability that are fully reversible (Nitsche et al., 2002). There are no known risks of tDCS to other than mild local discomfort at the electrode sites (much less than TMS for example). Several published studies on humans (Boggio et al., 2009; Gandiga et al., 2006; Hummel et al., 2005; Nitsche et al., 2003; 2004; Paulus, 2003; Uy & Ridding, 2003) reported the following objective safety data:

Date: March 2, 2021

Principal Investigator: [name], MA

Application Number: IRB00089018

- No heating of electrodes
- No demonstrable changes in the skin underlying electrode placement after a stimulation period similar to the one proposed in this protocol.
- Mild itching sensation in the absence of pain that never led to stopping a study.
- No change in serum neuron-specific enolase (NSE, marker for neuronal damage) in 5 participants immediately and 1 hour after exposure to 13 min of 1 mA anodal tDCS to motor cortex
- No changes in diffusion weighted or contrast-enhanced MRI and in EEG after exposure to tDCS (Nitsche et al., 2004).

Two reports, one evaluating the safety of tDCS applied in different brain regions in 102 healthy and stroke individuals (Poreisz et al., 2007) and another one investigating the safety of different forms and intensities of tDCS in 103 healthy participants (Iyer et al., 2005), concluded that tDCS is safe and only associated with relatively minor adverse effects in healthy and participants with different neurological conditions. In addition, a double-blind sham-controlled study has shown that comparing tDCS and sham stimulation of the motor cortex elicited minimal discomfort and difference in the duration of tingling sensations. There were no differences in self-rated attention or fatigue, and the study participants or investigators could not distinguish real tDCS from sham (Gandiga et al., 2006). Taken together, all available research suggests that prolonged application should not pose a risk of brain damage when applied according to safety guidelines.

MRI

The present study involves that participants undergo MRI scanning. The effects of undergoing MR scanning have been extensively studied and there are no risks associated with an MR exam. The patient may, however, be bothered by feelings of confinement (claustrophobia), and by the noise made by the magnet during the procedure. They will be asked to wear earplugs or earphones while in the magnet.

fNIRS

Near-infrared spectroscopy (NIRS) is a relatively new investigational tool. Although no adverse effects have been reported, it is possible that effects not yet reported may occur. The LED light in the NIRS devices used to make the measurements has low power (within the ANSI limit for long-term exposure to infrared light). Thus far, no hazard to patient, staff or third party has been observed. NIRS monitoring requires coupling “optodes” (optical sensors) to the skin on the scalp. This is achieved by fastening the optodes to a cap, placing the cap over the head and holding it in place with a strap placed under the chin or behind the head. The subject's hair may need to be parted in the location of the optodes to provide better coupling to the skin. The procedure does not cause pain or distress. Subjects will be asked to keep their head relatively still for several periods of up to approximately 10-15 minutes each while performing the tasks. However, the NIRS device will be made as insensitive as possible to head motion, and hence strict subject compliance is not essential. Fatigue and/or boredom from performing the tasks are the most likely risks in this study.

b. Steps taken to minimize the risks.

Participants will be carefully screened over the phone prior to being scheduled, to assure that they meet study criteria. tDCS stimulation will be ramped up over the first 15 seconds of stimulation in order to eliminate the sensation of tingling that can occur under the electrodes during the initial moments of tDCS

Date: March 2, 2021

Principal Investigator: [name], MA

Application Number: IRB00089018

application. The participant may stop testing or the intervention any time. There will be emergency personnel and equipment on hand for your safety.

c. Plan for reporting unanticipated problems or study deviations.

Adverse events will be monitored during the entire visit by the study team. The families will be given telephone numbers of study team as well. The study physician ([name]) and the DSMB will be notified immediately if any adverse events are reported. The DSMB will determine if the adverse event is a serious adverse event. Adverse events will be monitored until they are resolved or clearly determined to be due to a subject's stable or chronic condition or intercurrent illness. Medical care will be provided, as defined in the informed consent, for any adverse event related to trial participation. Appropriate medical care will include initiating transport to the Emergency Department of The Johns Hopkins Hospital for evaluation when necessary. All adverse events, regardless of intensity or causality, will be recorded in the study documentation and reported to the JHU IRB and DSMB. Any serious adverse events will be reported to the JHU IRB and the DSMB within 24 hours.

Plan for dealing with incidental findings: All MRI scans will be read by [name] who is willing to review our scans if there is anything new. Please note that ALL of our patients, who will be recruited from [name] database, have MRIs at different times post-stroke. If unexpected abnormalities - incidental findings - are seen (which is unlikely, as every patient will have had a clinical MRI as part of their evaluation for stroke), the patient will be asked permission to contact the primary care physician about the abnormality, and will be offered a timely appointment with a neurologist ([name], primary investigator) if appropriate.

d. Legal risks such as the risks that would be associated with breach of confidentiality.

Participation in this study should not put participants in any legal risk, even in the case of a breach of confidentiality. We will undertake every effort to keep the information in the study confidential. Participants will be assigned a code number for the scans in order to keep the information confidential. The computers on which the information will be stored are password protected. Everybody involved in the study will have completed the appropriate HIPAA training and are fully aware of confidentiality issues. No names will be included in any publications resulting from this work.

e. Financial risks to the participants.

No financial risk is involved. Only participants who are interested in trying word retrieval therapy with tDCS and can be in Baltimore for the therapy as well as the follow-up sessions will participate in the study.

9. Benefits

a. Description of the probable benefits for the participant and for society.

We cannot ensure that this research will provide any direct, sustainable benefit to the participants. It is possible that most participants will benefit from the present therapeutic intervention. Participants may or may not learn strategies to facilitate word retrieval and this knowledge may or may not generalize to other items or functions. Completion of this project will result in better understanding whether and how tDCS coupled with behavioral therapy may help individuals with post stroke aphasia.

10. Payment and Remuneration

a. Detail compensation for participants including possible total compensation, proposed bonus, and any proposed reductions or penalties for not completing the protocol.

Date: March 2, 2021

Principal Investigator: [name], MA

Application Number: IRB00089018

Participants will not be paid to participate in the study. There is no penalty for not completing a tDCS session. Participants will be reimbursed \$40 for travel and parking for each therapy session and evaluation session if they provide their own transportation. The study will provide sedan service (through Freedom Car sedan service) for patients who do not have transportation.

11. Costs

a. *Detail costs of study procedure(s) or drug (s) or substance(s) to participants and identify who will pay for them.*

There is no cost to the participants for participating in the study.

12. References

Banks, J. L., & Marotta, C. A. (2007). Outcomes validity and reliability of the modified rankin scale: Implications for stroke clinical trials: A literature review and synthesis. *Stroke; a Journal of Cerebral Circulation*, 38(3), 1091-1096. doi:01.STR.0000258355.23810.c6 [pii]

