After informed consent is received, a neurological examination will be performed and multiple screening assessments will be conducted including a tDCS and MRI safety screening (see below). If the participant passes the initial screening portion, speech and language diagnostic testing will be conducted during the same visit (Visit 1). During the next visit (Visit 2), participants will undergo a second baseline assessment of naming ability and assessment of connected speech. On that visit, participants who have no contraindication for MRI will be randomized to (1) fMRI electrode placement or (2) structural electrode placement. All participants who have no contraindication will have structural and rsfcMRI. Those randomized to fMRI electrode placement will also participate in the naming paradigm during the MRI. Participants may also undergo fNIRS at this visit. The third visit will include electrode positioning and tDCS treatment administration. Participants will receive 15 sessions (Visits 3-17) of tDCS + SALT administration. At the beginning of Visit 3, eligible participants will be randomized to receive either A-tDCS (1 mA) or sham-tDCS (placebo) for 15 sessions (20-minutes per each 45-minute behavioral treatment session) over the course of three weeks. A computer-delivered naming treatment will be coupled with the stimulation. The computer-delivered treatment task will be 45-minutes in total length, so that it will commence at the same time as the tDCS administration and continue for another 25-minutes after the tDCS has ceased. To assess cardiovascular arousal, blood pressure and heart rate will be measured before and after each session. Additionally, discomfort ratings will be recorded following the end of each session using the Wong-Baker FACES Pain Rating Scale (Wong & Baker, 1988) and a weekly neurological exam will be administered by a neurologist.

Neither the participant nor the clinician monitoring and setting up the treatment will have knowledge of the treatment condition (A-tDCS versus sham).

Date: March 2, 2021

Principal Investigator: [name], MA

Application Number: IRB00089018

Utilizing a computerized picture naming assessment (PNT), all participants will be assessed at several different time points throughout the experiment: twice immediately before and twice the week immediately following the fifteenth and final treatment session; twice at five weeks follow-up after the end of treatment; and twice at 20 weeks after the end of treatment.

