Both groups will receive SALT, which is the current clinical standard of care for post-stroke aphasia. It is currently unknown whether or not tDCS augments the effect of SALT in the subacute phase after stroke. Therefore, a sham group is justified.

f. Definition of treatment failure or participant removal criteria

Participants will be removed from the study if they are unable to comply with task instructions or tolerate the tDCS procedure.

g. Description of what happens to participants receiving therapy when study ends or if a participant's participation in the study ends prematurely

When the study ends participants will continue to receive management with [name] or their own neurologist as usual (generally follow-up visits every about 6). If a patient's participation in the study ends prematurely s/he will still receive care as before. In sum, termination of the study or termination of participation in it will not affect regular therapy he or she may be receiving.

Changes to Procedures in the Event of a Pandemic

Upon resumption of our clinical research investigating the use of transcranial direct current stimulation (tDCS) in subacute stroke in the wake of the COVID-19 emergency, we will take several precautions to minimize the risk of exposure to COVID-19 for our participants as well as for members of our research team. We will rely on these same contingencies in the event of another pandemic.

- For face-to-face visits, we will primarily use the STAR Car, a mobile lab space (wheelchair accessible van) that would allow for isolated testing in lieu of testing in participants' homes or in our

Date: March 2, 2021

Principal Investigator: [name], MA

Application Number: IRB00089018

testing rooms located at the hospital, thus minimizing the risk of possible exposure to COVID-19. If the STAR Car cannot be used for a particular session, we will perform home visits (preferably outdoors, e.g. on a porch if privacy is not an issue) to limit contact of participants with others at the hospital setting.

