5.2 Modified Intent-to-Treat Sample

All analyses will be done using the modified intent-to-treat principle (mITT). Under this principle, the evaluable sample will include all randomized participants for whom study treatment was initiated (e.g. attended at least one treatment session), regardless of the treatment actually received. Participants will be analyzed according to the group to which they were randomized. For secondary and exploratory analyses, missing data will not be explicitly imputed.

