5.3 Completers Sample

The primary analysis will be repeated using the subset of randomized participants for whom study treatment was initiated (e.g. attended at least one treatment session) and the PNT was collected at 1 week post-treatment. Participants will be analyzed according to the group to which they were randomized.

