8.2 Statistical Hypotheses

The Primary Hypothesis 1a: A-tDCS over a targeted region coupled with computer-delivered SALT is associated with greater gains in accuracy in naming pictures, compared to sham coupled with the same computer-delivered SALT in post stroke aphasia. To test this hypothesis, we will compare the change in means of outcome measures in the group who received sham versus the group who received tDCS. The primary outcome variable will be change in accuracy of naming untrained items within one week after treatment ends. The null hypothesis is $H_0: \mu_1 = \mu_2$, where μ_1 is the mean change in accuracy of naming untrained items (PNT correct) between baseline and 1 week post-treatment in the A-tDCS group and μ_2 is the mean change in the sham group. The primary analysis will compare change between groups (A-tDCS versus S-tDCS) using multiple regression and will be adjusted for aphasia type (Anomia, Broca, or other type), baseline aphasia severity (AQ), and age. The primary analysis will be performed using both the Completers and Modified Intent-to-treat Samples. If these two analyses are not consistent, then the trial findings will be interpreted with caution.

Sensitivity analyses will be done for the change in accuracy of trained items using the same approach. Naming errors will also be analyzed and categorized as semantic related, semantic unrelated, real words related phonologically, non-words related phonologically, mixed semantic/phonological, abstruse neologisms, and no response. Additional sensitivity analyses will adjust for education and time from stroke onset to time of treatment initiation in addition to the covariates included in the primary model.

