8.5 Missing Data

For the primary analysis, for participants who do not complete the 1 week post-treatment assessments, the post-treatment value will be imputed using a multiple imputation approach assuming a FCS missing mechanism and missing is at random (MAR).

As a sensitivity analysis with the modified ITT sample, the primary outcome analysis will be repeated using all available follow-up data (without explicit imputation) in a mixed effects model of the change from baseline in naming accuracy adjusted for baseline (with week (1, 5, or 20 weeks post-treatment) as class variable and a REPEATED statement). The model will include the baseline covariates used for the primary analysis as fixed effects.

The statistical model will be a repeated measures model (SAS® MIXED procedure with REPEATED subcommand) assuming a compound symmetry (CS) covariance structure.

```
PROC MIXED;
  CLASS SUBJID ARM VISITNUM TYPE;
  MODEL CHANGE= ARM|VISITNUM WABAQ TYPE AGE;
    REPEATED VISITNUM / TYPE= CS SUBJECT=SUBJID R RCORR;
  LSMEANS ARM*VISITNUM/pdiff CL;
RUN;
```

The least square (adjusted) mean for each treatment group, and the 95% confidence interval for the comparison (active vs. sham) will be presented at 1, 5, 20 weeks post treatment.

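### The Protocol's removal rule leaves it unclear whether participants who stop early still get the 1-week PNT; if they do not, no planned analysis checks the MAR assumption that fills the gap

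*Protocol*

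**What the plan says.** **Removal.** Protocol section 4f: "Participants will be removed from the study if they are unable to comply with task instructions or tolerate the tDCS procedure". The words are about leaving the study, not only the treatment. Section 4g, on premature end of participation, adds: "If a patient's participation in the study ends prematurely s/he will still receive care as before". It does not mention outcome assessment.

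**PNT schedule.** The overview in Protocol section 4a says that "all participants will be assessed at several different time points throughout the experiment", but fixes the first post-treatment PNT as "twice the week immediately following the fifteenth and final treatment session". A person who stops before session 15 has no such week.

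**Analysis samples.** Under SAP 5.2, "the evaluable sample will include all randomized participants for whom study treatment was initiated", whatever treatment they in fact received. SAP 5.3 defines Completers as those who attended at least one session "and the PNT was collected at 1 week post-treatment". It does not ask for 15 sessions.

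**Missing values.** SAP 8.5 fills a missing 1-week value by FCS multiple imputation under MAR. It does not list the variables in the imputation model. The sensitivity analysis is a mixed model on available follow-up without explicit imputation.

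**Consistency check.** SAP 8.2 runs the primary analysis in both samples: "If these two analyses are not consistent, then the trial findings will be interpreted with caution".

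**The concern.** Site staff could reasonably follow either reading. If they take 4f literally, the primary outcome is lost for people who stopped because they could not tolerate stimulation or manage the task. Such people may well differ in outcome from those who continue. Randomization takes place at the start of Visit 3, so intolerance of the assigned stimulation can appear only after assignment and could differ by arm.

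A participant removed after one or more sessions would stay in the modified ITT sample with an imputed value modelled on people who continued. The SAP's safeguard is agreement between the modified ITT and Completers results, and that agreement carries no information on whether MAR is right. The Protocol's own Missing Data paragraph recognizes that gaps in the primary outcome can be a problem.

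**Working it through.** **1. The plan's own figure.** Inputs from SAP 8.3: 20 per group, mean changes 33 and 10, SD 22.2, two-sided alpha 0.05. The noncentral t gives power 89.1% (normal approximation 90.6%) against the stated 89%. It reproduces, and this point does not dispute it.

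**2. What each planned analysis does with a removed participant who has no post-treatment PNT.**

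| Analysis | Treatment of that participant | Departs from MAR? |
|---|---|---|
| Modified ITT with multiple imputation | value predicted from observed participants | no |
| Completers regression | excluded | no |
| Mixed model | contributes no record | no |

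All three rest on essentially the same observed outcomes. With imputation by arm, the modified ITT and Completers analyses both have expectation 33 − 10 = 23, whatever the removed people truly gained. They would agree even where MAR is false.

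**3. Size, as an illustration.** The documents give no removal rate by arm or reason. Assumptions: k active participants are removed without a PNT, their true mean gain is 10 (the planned sham gain), the others gain 33, and covariates are ignored.

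- A: imputation by arm, 25 per arm including the removed. Overstatement = (k/25) × (33 − 10).
- B: imputation by arm, 25 per arm with an observed PNT (the goal in SAP section 4) and removals on top. Overstatement = k/(25 + k) × 23.
- C: as A, but arm left out of the imputation model. Imputed mean M = [(25 − k) × 33 + 25 × 10]/(50 − k), which is 21.27, 21.02 and 20.22 for k = 1, 2 and 5. Overstatement = (k/25) × (M − 10).
- SE under A = 22.2 × √(1/(25 − k) + 1/25).

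| k | A | B | C | SE (A) | A/SE |
|---|---|---|---|---|---|
| 1 | 0.92 | 0.88 | 0.45 | 6.34 | 0.15 |
| 2 | 1.84 | 1.70 | 0.88 | 6.41 | 0.29 |
| 5 | 4.60 | 3.83 | 2.04 | 6.66 | 0.69 |

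The row k = 5 is a weakly anchored extreme. The Protocol expects 40 to 45 of 50 to complete, so 5 to 10 do not, but that covers all reasons, both arms and possibly losses after week 1.

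The true differences under A are 23 − 0.92 = 22.1 and 23 − 1.84 = 21.2 for k = 1 and 2. The critical differences, t(0.975; 48 − k) × SE, are 12.76 and 12.91, so the expected result stays significant.

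**4. Why arm belongs in the model.** The smaller bias in C is not a merit. If MAR is true and two removed active participants would have gained 33, leaving arm out understates the effect by (2/25) × (33 − 21.02) = 0.96 items.

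**5. No treatment effect.** In 10,000 simulated trials (normal imputation by arm, 20 imputations, no covariates, two removed per arm), the bias was 0.0. Type I error was 4.8% when the removed gained the same as others and 4.6% when they gained 10 less in both arms. These runs cover balanced removal only.

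**The case against.** The strongest reply is that the governing text already leans towards collection. The Protocol overview speaks of all participants, SAP 5.2 keeps everyone who started, and SAP 5.3 makes best sense if a PNT can exist without 15 sessions. Section 4g is headed as a question about people receiving therapy, so an answer about care is what one would expect there. The consent pages were not available and may say more. This stands in part: a reader might infer that the plan sets out to discard outcomes of early stoppers, and the documents do not support that. What remains is a conflict. SAP section 2 gives the final SAP precedence over the Protocol, but a sample definition does not tell site staff to bring back someone whom 4f has removed from the study.

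It is also fair that few removals are likely. Task comprehension and tDCS safety are screened at Visit 1, scalp sensitivity is an exclusion, and Protocol sections 3 and 8a report good tolerability.

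A reader might further infer that the gap could produce a false positive trial. In simulations at the design effect (arrangement A), the MAR analysis was significant and a reference-based one was not in 1.0%, 2.7% and 12.2% of trials for k = 1, 2 and 5. But tDCS truly works in all of those trials, so rejecting the null is correct in each. They show no wrong conclusion.

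Finally, an analysis that departs from MAR needs a parameter that the documents do not supply. That is a fair reason to treat it as optional.

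**Conclusion.** The point holds as an unreconciled conflict about outcome collection, together with an untested MAR assumption. No visible passage provides for a PNT after removal under 4f, and no planned analysis departs from MAR, so agreement between the modified ITT and Completers results should not be read as support for it.

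Bias is possible, not shown, and probably small: about 0.9 items for one removed active participant and 1.7 to 1.8 for two, against a planned difference of 23. This rests on removed participants gaining 10 rather than 33, removals only in the active arm, and imputation by arm. With arm omitted it is about half. No inflation of type I error has been shown. This is a worthwhile, inexpensive improvement and not a flaw that undermines the trial.

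**What to change.** Leave the criteria for stopping stimulation or therapy as they are.

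- **Protocol.** Reconcile 4a, 4f and 4g with SAP 5.2 and 5.3 by stating that ending study treatment does not end outcome collection. The PNT is still sought at 1, 5 and 20 weeks, counted from the scheduled end of treatment, unless consent is withdrawn or the test cannot be done.
- **SAP 5.2 and 8.5.** State that PNT values observed after early stopping are used in the modified ITT analysis, that only values still missing are imputed, and that treatment arm is in the imputation model.
- **Optional.** Add one delta-adjusted or reference-based sensitivity analysis for values still missing, with its parameter chosen and justified before unblinding.

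The cost is one sentence in the Protocol and two or three in the SAP. The time points are already scheduled, and the pandemic procedures describe a remote format. The downside is a few extra assessments of people who stopped treatment, some of whom will decline or be unable to do the PNT. Collection can help only participants who have not yet finished. The SAP wording can still change, because SAP section 2 foresees an update before database lock.
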